*If a patient is discharged then these assessments may not be performed.

@Whilst an inpatient, participants should have a daily assessment for evidence of nausea, vomiting, diarrhoea, bloating and abdominal pain. This information will be collected for outpatients in the patient questionnaire.

& If a participant is not discharged at Day 14 and remains in hospital, Day 14 assessments will be performed until a participant is discharged from hospital or they reach the final follow-up visit (Day 42).

¹ Pregnancy test will only be performed in women of child-bearing potential (Appendix 2).

² If the patient is on 3L/min oxygen flow or less, this assessment should be performed after the patient is at rest on room air for 10 minutes, as detailed in section 8.1.1.

³ If the patient is discharged prior to these blood tests, where possible outpatient blood testing will be organised.

⁴ Extraction of relevant clinical data from the patient's medical record (such as but not limited to symptoms, concomitant medications, other relevant blood tests, and radiology reports such as chest radiograph or CT scan).

⁵ If the patient is discharged, they will be given a daily questionnaire to complete; a telephone call will be made on day 7, 14, 21 and 42 (telephone call has a window of +/- 1 day).

⁶ The patient will be asked to continue to fill the questionnaire daily until their symptoms have fully resolved for 48 hours or until the day 42 telephone visit (whichever is earlier).

⁷ This is an optional sample for research purposes but will be collected whenever possible once at the Baseline visit and then again once between Days 5-14. If the patient is discharged prior to this faecal test, where possible, an outpatient sample will be collected.

⁸ Administered twice daily for six doses) and then once daily for the remaining days (17 doses total). Treatment will be stopped if the participant is admitted to ICU, meets individual stopping criteria, or is withdrawn from the study.

⁹ Smoking status to include whether current-smoker, ex-smoker, or never-smoker; and to quantify current usage and total pack-year history.

2. Introduction

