
To evaluate the effect of EDP1815 on length of hospitalization and recovery in participants with COVID-19	
Time to discharge, defined as the time in days from start of treatment to first occurrence of a WHO OSCI score of 2 or less.Time to oxygen saturation (SpO_2) $\geq 94\%$ on room air without further requirement for oxygen therapy.Time to recovery, defined as the time in days from symptom onset to alleviation of all COVID-19 symptoms.

To evaluate the safety and tolerability of EDP1815 in participants with COVID-19	
Incidence and severity of treatment emergent adverse events and serious adverse events.Incidence of clinically significant abnormal changes in safety laboratory parameters.
Exploratory	

To evaluate the effect of EDP1815 on the exaggerated host cytokine response to COVID-19 infection	
Change from baseline in cytokine levels (including IL-6) at day 4 and day 7 (and/or at additional timepoints if samples are available).Change from baseline in inflammatory response at day 4 and day 7 (and/or at additional timepoints if samples are available).

To identify clinical or biochemical predictors of response to EDP1815, and to confirm lack of systemic absorption.	
Statistical significance of each potential predictor-treatment interaction in exploratory models based on the final selected model for the primary efficacy analysis.To identify the presence of EDP1815 in stool and/or blood using PCR primers

4. Study Design

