5.3.3.4 WHO OSCI

The WHO OSCI has values ranging from 0 to 8 as shown in [Table 6](#).

Table 6 WHO Ordinal Scale for clinical Improvement

Participant State	Descriptor	Score
Uninfected	No clinical or virological evidence of infection	0
Ambulatory	No limitation of activities	1
	Limitation of activities	2

Participant State	Descriptor	Score
Hospitalized – Mild disease	Hospitalized, no oxygen therapy	3
	Oxygen by mask or nasal prongs	4
Hospitalized – Severe Disease	Non-invasive ventilation or high flow oxygen	5
	Intubation and mechanical ventilation	6
	Ventilation + additional organ support	7
Dead	Death	8

The WHO OSCI will be recorded daily in the eCRF while participants remain in hospital. Once discharged, the WHO OSCI will be derived from questions 1 and 2 of the daily COVID-19 diary using the rules defined in [Table 7](#).

Table 7 Derivation of WHO OSCI using the Outpatient Daily Covid-19 diary

Question 1: Overall, how severe were your COVID-19 symptoms today?	Question 2: How much did your COVID-19 symptoms interfere with your usual activities today?	WHO OSCI Score
No COVID-19 symptoms today	Any response	0
Mild, moderate, severe or very severe	Not at all	1
Mild, moderate, severe or very severe	Somewhat or Very much	2

For participants who report question 1 as “No COVID-19 symptoms today” and a return to their usual activities (Q3) for 2 days in a row do not need to complete the COVID-19 diary on subsequent days. If this condition is met, the missing WHO OSCI score will be imputed as 0 for any remaining study days up to and including Day 42.

Note that participants who are discharged on home oxygen will still be considered as having WHO OSCI score =2 as the participant state is considered before the descriptor in [Table 6](#).

For participants who die, the WHO OSCI score will be imputed to 8 for all remaining study days after death.

WHO OSCI scores that are missing for reasons other than death or full recovery of symptoms will not be imputed.

For the secondary endpoint looking at whether participants remained at or below their baseline WHO OSCI score at Days 4, 7, 10, 14, 21 and 42, participants who show an increased score and then return to their baseline score (or lower) will not be considered as having met the criterion for this endpoint. Only participants who have not reported a score above their baseline score on any day prior to the endpoint day will be considered as having met the endpoint for that day.

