5.3.3.5 Overall Survival and Intubation and Mechanical Ventilation Free Survival

Overall survival (OS) is defined as the time in days from randomization until death by any cause.

Intubation and mechanical ventilation free survival (IMVFS) is defined as the time in days from randomization until the earliest event of death by any cause or requirement for intubation and/or mechanical ventilation as indicated by the first occurrence of a WHO OSCI score of 6 or above.

Participants who complete the 42-day study period or prematurely withdraw from the study without experiencing the relevant event will be censored on the date of study completion/withdrawal.

Participants who prematurely withdraw from treatment but remain in the study will not be censored and will continue to be followed up until the first occurrence of the relevant event, study completion or withdrawal from the study.

Time to the relevant event will be calculated as:

$$\text{Time to event (days)} = \text{Date of event/censoring} - \text{date of randomization} + 1$$

5.3.3.6 Time to Discharge, Time to SpO2 ≥94% on Room Air and Time to Recovery

Time to discharge is defined as the time in days from randomization until the date of discharge.

Time to SpO2 ≥94% on room air is defined as the time in days from randomization to the first day at which an SpO2 measurement ≥94% on room air is reported after which there were no further requirements for oxygen therapy during the study.

Time to recovery is defined as the time in days from the date of symptom onset until the first day on which a WHO OSCI score of 0 is reported with no further increase above 0 during the study.

Participants who die during the study before the relevant event occurring will be given a status of 'death' which will be considered as a competing risk rather than an event or a censored observation in the analysis.

Participants who are still alive at the end of the 42-day study period or who withdraw prematurely from the study for reasons other than death without experiencing the relevant event will be censored on the date of study completion/withdrawal.

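### Time to recovery is symptom alleviation in the protocol and in SAP Table 1, but SAP 5.3.3.6 counts a sustained OSCI of 0, which cannot occur before discharge and so mixes symptom resolution with discharge

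*SAP*

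**What the plan says.** - **Protocol section 3, Table 2** (the same text is in synopsis Table 1): "Time to recovery, defined as the time in days from symptom onset to alleviation of all COVID-19 symptoms". It sets no condition on whether the participant is in hospital. SAP Table 1 repeats this wording.
- **SAP 5.3.3.6** gives the operational rule: the time runs from symptom onset "until the first day on which a WHO OSCI score of 0 is reported with no further increase above 0 during the study".
- **SAP 5.3.3.4, Table 6**: score 0 is the uninfected state, "No clinical or virological evidence of infection". The lowest hospitalized row is 3, "Hospitalized, no oxygen therapy". Home oxygen does not move a discharged participant back into the hospitalized rows, "as the participant state is considered before the descriptor in" that table.
- **SAP 5.3.3.4** on data source: "The WHO OSCI will be recorded daily in the eCRF while participants remain in hospital". After discharge the score is derived from the diary (Table 7), where a report of no symptoms gives 0.
- **Protocol section 3** defines time to discharge as running "from start of treatment to first occurrence of a WHO OSCI score of 2 or less".
- **SAP 9.3.5.1, Table 13** says that, for time to recovery, actual values are used whether the participant is an inpatient or an outpatient.
- **SAP section 14** (changes to the protocol) says not applicable.

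**The concern.** The protocol event can happen in a hospital bed. The SAP event cannot. A participant who is symptom free on Day 8 and discharged on Day 12 recovers on Day 8 by the protocol, and only after Day 12 by the SAP. The SAP also carries both definitions, in Table 1 and in 5.3.3.6, and declares no change.

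Shortening the time to symptom resolution is one of the aims in the protocol's overall design, and this is the only time-to-event endpoint that addresses it. Time to discharge is already a separate endpoint. The pilot is also meant to show which endpoints are sensitive enough to take into later trials. If the recovery result partly reflects discharge practice, a reader could credit the product with a symptom effect that is really earlier discharge, or could miss part of a real symptom effect.

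**Working it through.** The documents give no event rate, power or precision figure for time to recovery, so there is no stated figure to reproduce. The check has two parts.

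**1. Definitions (no assumptions).** Let S be the first symptom-free day and D the discharge day.

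- Protocol event day = S.
- Table 6 puts states 3-7 in hospital, and the SAP considers state before descriptor. The protocol treats a score of 2 or less as discharge. A 0 therefore implies that the participant has been discharged.
- The only symptom-based route to 0 is Table 7. SAP 5.3.2.8 expects the diary on days following discharge, so the first diary day is D + 1.
- SAP event day = max(S, D + 1), provided that no later score is above 0.

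With D = 8:

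| S | Protocol day | SAP day | Delay (days) |
|---|---|---|---|
| 4 | 4 | 9 | 5 |
| 6 | 6 | 9 | 3 |
| 8 | 8 | 9 | 1 |
| 9 | 9 | 9 | 0 |
| 12 | 12 | 12 | 0 |

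If the participant is symptom free but still in hospital at Day 42, the protocol has an event at S and the SAP censors.

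**2. Possible size (all inputs assumed).** S and D are Weibull with shape 1.5, linked by a Gaussian copula with correlation 0.3-0.6. Median discharge is 8 days, and times are counted from randomization. The SAP event is taken as max(S, D). The apparent hazard ratio is ln[P_active(not recovered by m)] / ln[P_control(not recovered by m)], where m is the control median of the SAP event.

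| Assumed median symptom resolution | Symptom free before discharge | Rise in median time | Symptom HR 1.5 appears as | Discharge-only HR 1.5 appears as |
|---|---|---|---|---|
| 6-12 days | 27-67% | 1.2-3.8 days | 1.13-1.38 | 1.10-1.34 |
| 14-18 days | 13-27% | 0.3-1.6 days | 1.40-1.47 | 1.01-1.11 |

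To read these figures: at the control median, a hazard ratio of 1.5 leaves 0.5^1.5 = 35% of the active arm not recovered. An apparent 1.47 leaves 0.5^1.47 = 36%, and an apparent 1.13 leaves 0.5^1.13 = 46%.

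**Cross-check with another model.** Here the times are log-normal (log-SD 0.6, correlation 0.5, median discharge day 6) with the SAP event at max(S, D + 1). Entries in the last two columns are mean differences, active minus placebo.

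| Median symptom-free day | Symptom free by discharge | Discharge 25% shorter, symptoms unchanged: SAP difference (protocol about 0) | Symptoms 25% shorter: protocol difference, then SAP difference |
|---|---|---|---|
| 14 | 10% | -0.3 days | -4.2, then -3.7 days |
| 10 | 24% | -0.5 days | -3.0, then -2.3 days |
| 7 | 46% | -1.0 days | -2.1, then -1.1 days |
| 5 | 68% | -1.3 days | -1.5, then -0.5 days |

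Both models agree in direction, and in both the distortion grows with the share symptom free before discharge. Neither models death, which the SAP treats as a competing risk. The Weibull model also counts from randomization, whereas the SAP counts from symptom onset.

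**The case against.** The best defence is that the SAP makes a loosely worded endpoint computable. The protocol names no data source, no persistence rule and no inpatient symptom measure, and its section 9.3.2 leaves estimand details to the SAP. The Schedule of Activities has no daily inpatient symptom assessment, and the symptom diary starts only at discharge. The OSCI is the one daily clinical-status scale that spans both settings. After discharge, Table 7 makes a 0 equivalent to no symptoms that day. All of this stands. It explains the rule, but not why the result keeps the name and Table 1 wording of symptom alleviation with no change declared.

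Four stronger readings are tempting, and the documents do not support them:

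- *The symptom aim goes untested, or the endpoint merely repeats time to discharge.* For anyone still symptomatic at discharge, the event is set by symptoms. The protocol plans for such participants by continuing the diary until they are symptom free for 48 hours or reach Day 42. In the simulations a symptom effect is reduced but still visible.
- *The distortion must be large.* It is large only if many are symptom free before discharge, and no document says how many are.
- *Requiring no later rise above 0 is an error.* It is a reasonable reading of alleviation of all symptoms and parallels the no-further-oxygen condition in the SpO2 endpoint. It only needs declaring.
- *Inpatient symptom dates are already collected.* Schedule footnote 4 covers one retrieval, marked at Day 42, of items "such as but not limited to symptoms, concomitant medications, other relevant blood tests" and so on. Nothing says that absence of symptoms is charted or dated daily.

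One limit also applies to the point itself. No sentence forbids a site from entering 0 for an inpatient. That bar follows from the scale, the state-before-descriptor note and the protocol's definition of discharge.

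**Conclusion.** The point holds as a conflict of definition, at minor severity. Followed as written, SAP 5.3.3.6 dates recovery at the later of symptom resolution and discharge, in practice no earlier than about the day after discharge. That conflicts with the protocol and with SAP Table 1. This part rests on the documents alone.

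The size is uncertain. Over assumed median symptom resolution of 6-18 days against a median discharge of 8 days, the apparent symptom hazard ratio runs from almost undiluted (1.47 for a true 1.5) to mostly lost (1.13). The apparent recovery effect of a discharge-only benefit runs from negligible (1.01) to substantial (1.34). The documents give nothing that would place the trial within that range.

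The consequence is limited. The endpoint is secondary, all analyses are descriptive, no primary conclusion depends on it, and time to discharge is reported alongside. What changes is the claim that the result can carry: it describes being home and free of symptoms, not symptom recovery alone.

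**What to change.** Before database lock:

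1. In SAP 5.3.3.6, SAP Table 1 and the titles of the related outputs (Table 14.2.9, Figure 14.2.9, Listing 16.2.6.7), rename the endpoint 'time to discharged and symptom free'. State that it is not to be read as symptom recovery alone.
2. Report by arm the number and percentage already at OSCI 0 on their first post-discharge diary day. When the 0 is sustained, discharge sets the event time for these participants. The count slightly overstates the group affected, because someone whose symptoms end exactly on that day is dated the same under both definitions.
3. Keep the no-later-rise condition, but declare it.
4. Record the change of definition in SAP section 14, and align the wording of Table 13, which implies that the event can be observed in hospital.
5. Treat dating of recovery from inpatient chart symptoms as a supportive analysis at most, and only if the records prove to be dated well enough. Joining chart inference to a self-reported diary would itself create a break in measurement at discharge.

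The cost is SAP wording and one extra count from diary data already collected. No new data collection is needed.

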5.3.3.7 Number of Days Requiring Oxygen Therapy

For participants who are discharged with ongoing oxygen therapy, any changes to their oxygen therapy are to be reported in the participant diary they complete daily. This data will be transcribed to the oxygen therapy page of the main CRF.

Each study day will be flagged as with or without oxygen therapy based on the start and stop dates for relevant records in oxygen therapy page. For example, if a record for oxygen therapy is shown as starting on Day 2 and ending on Day 6 then Days 2-6 inclusive will all be flagged as with oxygen therapy.

Number of days with oxygen therapy will be reported for the following intervals:

- Days 1-14
- Days 1-28
- Days 1-42

For each interval, the percentage of days with oxygen therapy will be calculated, using the number of days in the interval prior to death or premature withdrawal as the denominator.

For participants who die or withdraw prematurely from the study, a sensitivity variable will be created which counts study days after death/early withdrawal as 'with oxygen therapy' up to Day 42.

5.3.3.8 Temperature and Number of Days with Pyrexia $\geq 38^{\circ}\text{C}$

Temperature will be reported daily for participants prior to discharge. The daily temperature reported on the CRF should be the highest recorded in the participant notes for that day.

After discharge, participants are asked to report their temperature daily while they are still experiencing symptoms if they have a thermometer at home. If they do not have a thermometer at home, they should answer a question on the daily diary to say if they feel like they have a fever.

In the event that a subject reports data in both the patient diary and on the vital signs CRF for a single study day, both measurements will be listed but the temperature collected on the CRF vital signs page will be used in the tables and figures.

Temperature may be recorded in $^{\circ}\text{C}$ or $^{\circ}\text{F}$. Temperature recorded in $^{\circ}\text{F}$ will be converted to temperature in $^{\circ}\text{C}$ as follows:

$$\text{Temperature } (^{\circ}\text{C}) = (\text{Temperature } (^{\circ}\text{F}) - 32) * (5/9)$$

Temperature ($^{\circ}\text{C}$) will be presented to 1 dp in the listings.

Each study day will be flagged as with or without pyrexia $\geq 38^{\circ}\text{C}$ based on the actual data reported.

Number of days with pyrexia $\geq 38^{\circ}\text{C}$ will be reported for the following intervals:

- Days 1-14
- Days 1-28
- Days 1-42

For each interval, the percentage of days with pyrexia $\geq 38^{\circ}\text{C}$ reported will be calculated, using the number of days with a temperature measurement recorded as the denominator.

As temperature data is expected to be missing not at random (MNAR), i.e. that the reason for missingness may be dependent on the missing value (were it to have been observed), an alternative method for counting days with pyrexia will be used for sensitivity analyses as detailed below:

- Missing temperature measurements because a participant has died or withdrawn from the study
 - Days after death/withdrawal will be counted as having pyrexia $\geq 38^{\circ}\text{C}$
- Missing temperature measurements while participant is still in hospital
 - If there exists at least one temperature measurement within 1 day of the missing measurement, it will be imputed with the average of the measurements reported within the window of $+\text{-} 1$ day
 - If there is no recorded temperature on the day before or after the missing measurement, then carry forward the response from the last day on which temperature was measured.
- Missing temperature after participant was discharged
 - If the participant has answered the question 'Do you feel like you have a fever?' as 'Yes' then count the day as with pyrexia $\geq 38^{\circ}\text{C}$
 - If the participant has answered the question 'Do you feel like you have a fever?' as 'No' then count the day as without pyrexia $\geq 38^{\circ}\text{C}$
 - If the participant had stopped completing the daily diary as they had already reported no after 2 consecutive days of no symptoms and a return to their usual activities, then count the day as without pyrexia $\geq 38^{\circ}\text{C}$
 - Otherwise carry forward the response from the last day on which either temperature was measured or the daily diary question about fever was answered

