5.3.2.8 Daily Diary Compliance

The daily diary should be completed on every day following discharge from hospital until the participant has reported at least two consecutive days with no symptoms (Q1) and a return to their usual activities (Q3).

The last day on which a daily diary is expected is defined as the earliest of the second consecutive day on which the participant reported no symptoms and a return to their usual activities and Day 42/Study day of early withdrawal from the study.

The number of days on which a daily diary is expected will be defined as:

Number of diary days expected = Date of last expected diary day – Date of discharge

The number of diary days completed will include all days on which at least questions 1-3 of the diary were answered up to and including the date of the last expected diary day. Diary days completed after Day 42 or after the second consecutive day with no symptoms and a return to their usual activities will not be included.

Daily diary compliance will be calculated as:

Daily diary compliance (%) = $100 \times \text{Number of diary days completed} / \text{Number of diary days expected}$

Daily diary compliance will be presented to 1 dp in the listings.

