9.3.6 Other Secondary Endpoints

Number and percentage of days requiring oxygen therapy and the sensitivity variable described in [Section 0](#) will be summarized for days 1-14, 1-28 and 1-42 and listed. Details of all oxygen therapy used will also be listed.

Number and percentage of days with pyrexia ≥ 38°C and the sensitivity variable described in [Section 5.3.3.8](#) will be summarized for days 1-14, 1-28 and 1-42 and listed. Maximum temperature for each participant will also be summarized. Daily temperature data will also be listed.

Minimum and maximum SpO₂ for each participant will be summarized and listed. Daily SpO₂ values will be included in the listing of daily S/F ratio data.

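### The main percentage of days with pyrexia uses only days with a recorded temperature as its denominator, so for a given number of fever days a faster recovery or discharge gives a higher percentage

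*SAP*

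**What the plan says.** Protocol Section 3 and SAP 4.2 list the number of days with pyrexia ≥38 °C as a secondary endpoint. SAP 5.3.3.8 adds a percentage for Days 1-14, 1-28 and 1-42. Days are flagged "based on the actual data reported", and the percentage is formed "using the number of days with a temperature measurement recorded as the denominator".

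The same section sets out when a temperature exists. In hospital, "Temperature will be reported daily for participants prior to discharge". Afterwards, "participants are asked to report their temperature daily while they are still experiencing symptoms if they have a thermometer at home". Two other places fit with this:

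- Protocol 1.3 marks vital signs with the footnote "If a patient is discharged then these assessments may not be performed".
- SAP 5.3.2.8 has the diary kept "until the participant has reported at least two consecutive days with no symptoms" and usual activities resumed, or until Day 42 or withdrawal.

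A participant who stays in hospital past Day 14 continues with the Day 14 assessments until discharge or Day 42 (Protocol 1.3, footnotes).

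SAP 5.3.3.8 expects temperature to be missing not at random and defines a sensitivity count. That count treats days after the diary has ended for recovery as without pyrexia, uses the diary fever question where there is no temperature after discharge, and treats all days after death or withdrawal as with pyrexia. SAP 9.3.6 reports the number, the percentage and the sensitivity variable for the three intervals.

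**The concern.** Whether a day enters the denominator depends on how the participant is doing. Prolonged hospitalization fills it with days, while recovery, or discharge without a thermometer, empties it. The days removed by recovery are the ones the SAP itself regards as fever free in its sensitivity rule.

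The neighbouring percentage avoids this. For oxygen therapy, SAP 5.3.3.7 divides by the interval days before death or withdrawal. Two adjacent percentage-of-days summaries over the same intervals thus rest on different denominators, with no reason given.

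At stake is a misleading descriptive comparison. If EDP1815 shortens illness, its percentage can look no better, or worse, than placebo while its participants have the same number of fever days or fewer. The pilot is meant to judge endpoints for relevance and sensitivity for later studies (SAP Section 6). The pyrexia table, 14.2.11, is also marked for the unblinded efficacy review at which the monitoring committee considers 40 more participants (SAP 7.4.2 and Appendix 1).

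**Working it through.** The documents give no figure for this percentage, so there is none to reproduce. The rules come from SAP 5.3.3.8, 5.3.2.8 and 5.3.3.7. All participant values below are assumptions.

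**1. Direction.** Let F be days ≥38 °C and D be days with a recorded temperature. The planned percentage is 100 × F/D. Comparing a faster-recovering case (F′, D′) with a slower one (F, D), the ratio of percentages is (F′/F) ÷ (D′/D).

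- It exceeds 1 when fever days fall proportionally less than recorded days.
- It equals 1 when they fall equally.
- It is below 1 when fever days fall more, but the benefit is then understated, because F′/F is divided by a number below 1.
- With F = 0 the percentage is 0% whatever D is.

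| Faster | Slower | Reading |
|---|---|---|
| 3/8 = 37.5% | 3/20 = 15.0% | same fever days, higher percentage |
| 2/6 = 33.3% | 4/14 = 28.6% | half the fever days, still higher |
| 1/6 = 16.7% | 4/14 = 28.6% | lower, but the ratio is 0.58, against 1/4 = 0.25 in fever days |

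**2. Example for the three planned intervals.**

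- A has fever on Days 1-3 and temperatures on Days 1-6, is discharged, is symptom free with usual activities on Days 7 and 8 (no temperature is requested on those days), and so meets the recovery rule on Day 8.
- B has fever on Days 1-8 and stays in hospital to Day 42 with a temperature every day.

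Counting A's post-recovery days, from Day 9 on, as fever free adds 42 − 8 = 34, 28 − 8 = 20 or 14 − 8 = 6 days to A's 6 recorded days. B does not change.

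| Interval | A, planned | A, recovery days counted | B, either way |
|---|---|---|---|
| Days 1-42 | 3/6 = 50.0% | 3/40 = 7.5% | 8/42 = 19.0% |
| Days 1-28 | 3/6 = 50.0% | 3/26 = 11.5% | 8/28 = 28.6% |
| Days 1-14 | 3/6 = 50.0% | 3/12 = 25.0% | 8/14 = 57.1% |

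The planned rule reverses the ranking over Days 1-42 and Days 1-28. Over Days 1-14 it keeps the ranking but compresses the contrast: A/B is 50.0/57.1 = 0.88 instead of 25.0/57.1 = 0.44.

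**3. Group-level illustration.** This is a simulation with a mean of about 16 recorded days and 3 fever days in the slower group, and recording 30% shorter in the faster group. The slower group's values are 24.3-24.4% on recorded days and 7.1% on a fixed 42-day denominator.

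| Fall in fever days | Faster group, recorded days | Faster group, fixed 42 days |
|---|---|---|
| 0% | 33.4% | 7.0% |
| 10% | 30.5% | 6.3% |
| 20% | 27.3% | 5.6% |
| 30% | 24.1% | 5.0% |
| 40% | 20.8% | 4.3% |

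Under these assumptions, a 20% reduction in fever days appears as a rise from 24.3% to 27.3%, and a 30% reduction almost disappears. This matches the condition in step 1.

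**4. Does the sensitivity variable resolve it?** It applies the recovery rule, but together with the rule that days after death or withdrawal count as pyrexia. A withdrawal on Day 10, for example to enter another trial after ICU admission, adds 42 − 10 = 32 such days over Days 1-42. It is described as a way of counting days, and no denominator is stated for a percentage.

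**The case against.** The strongest reply is that the percentage is not the endpoint. The endpoint is the number of days, for which Protocol 9.3.2 asks only for summary statistics. A reader sees 3 days for A and 8 for B, ranked correctly. No model or test uses the percentage, and SAP Section 9 calls all analyses descriptive. The SAP also acknowledges the informative missingness and reports a sensitivity variable. All of this stands and sets the weight of the point, but it does not change what the main percentage shows.

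Stronger readings are tempting, and the documents do not support them:

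- *Faster recovery always raises the percentage.* It does not: see the 1/6 against 4/14 case and the Days 1-14 row.
- *The percentage is too high by a fixed multiple.* The gap in the example is between a share of recorded days and a share of mostly interval days for one constructed participant. It does not estimate bias between arms.
- *The sensitivity variable is worthless.* Its worst-case rule affects only those who die or withdraw; for everyone else the recovery rule works as intended. The gap is the unstated denominator and the bundling of the two rules.
- *Leaving the diary fever answer out of the main count is an error.* Keeping a subjective answer out of a measured threshold of ≥38 °C is a defensible choice.

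The comparison with oxygen is also not exact. Oxygen status follows from start and stop dates, so every day has one, whereas temperature has true gaps. That argues against simply dividing by all interval days, and the fix allows for it.

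**Conclusion.** The point holds in conditional form. Followed as written, SAP 5.3.3.8 removes fever-free days from the denominator as participants recover or go home without a thermometer. For a given number of fever days, the faster course then gets the higher percentage. In general, the comparison is reversed or weakened according to how fever days and recorded days fall relative to each other.

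The example sizes (50.0% against 19.0% as planned, 7.5% against 19.0% with recovery days counted, Days 1-42) rest on assumed courses and show the mechanism, not an expected bias. They also assume that participants record temperature when asked and not otherwise; voluntary recording after recovery would reduce the effect.

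The importance is low to moderate: a supplementary descriptive percentage beside an unaffected count. It is worth correcting because it is reported for three intervals, belongs with a table the monitoring committee will see, and can be corrected with a rule the SAP already contains.

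**What to change.** In SAP 5.3.3.8:

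1. For the main percentage, count days after the two-day recovery rule as without pyrexia and include them in the denominator, up to death or withdrawal as in 5.3.3.7.
2. Leave other days without a temperature out of the main denominator and report how many there are by arm and interval, so that they are not silently treated as fever free.
3. Keep the diary fever answer and the worst-case rule for death and withdrawal in the sensitivity variable, and state its denominator as all days in the interval.
4. Keep the recorded-days percentage as a supplementary summary, labelled as such.

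The number of days with pyrexia stays as the endpoint. The handling of deaths does not change, since the main percentage already takes no days after death and the sensitivity variable keeps the worst-case value.

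The cost is SAP wording, a small change to one derivation and an added line in the table; no new data are needed. It is best done before the efficacy outputs for the 60-participant review are produced. The downside is that the main percentage then relies on recovered participants staying fever free, and days at home with symptoms but no thermometer remain outside it.
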